2.2 Neuroimaging Sub-Study

Aim 1: Identify putative brain mechanisms underlying BAS+ (vs. SC) treatment for smoking cessation and PCWG.

H1a: BAS+ (vs. SC) will decrease food cue-induced activity in insula, anterior cingulate cortex (ACC), orbitofrontal cortex (OFC), and ventral striatum/accumbens (VS/NAC);

H1b and H1c: (Hb) BAS+ (vs. SC) will decrease food reinforcement choice-related activity in VS/NAC and ventromedial prefrontal cortex (vmPFC); and **(H1c)** will produce corresponding decreases in food craving, reward, and reinforcement at the behavioral level (task performance).

Aim 2: To evaluate the relative contribution of treatment-induced changes in task related brain signal (Food Cue Response, Food Reinforcement/Choice) in prediction of post treatment food intake.

H2a: Brain network response (H1a-b) in the BAS+ (vs. SC) group will characterize treatment-induced changes in caloric intake (and quit success) more accurately than clinical (age, sex, nicotine dependence, BMI) and behavioral (withdrawal, craving, food reinforcement) measures alone.

H2b: The relative contribution of domain specific brain signal (food cue reactivity and food reward) to the prediction of treatment-induced change in caloric intake will be evaluated (regression model).

Aim 3: Test whether BAS+ (vs. SC) induced change in neural responses to food cues and food reinforcement is a stronger predictor of food intake among smokers with greater cognitive control.

We predict that the relationship of food cue and choice-related neural activity (e.g., VS/NAC BOLD signal; BAS+ vs. SC) will be a stronger predictor of caloric intake among smokers who also show greater working memory-related neural activity (i.e., DLPFC BOLD signal) at baseline and post treatment. Regions of interest for food cue and choice-related neural activity will be selected from those shown to be sensitive to cessation in Aim 1.

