6.8 Sample Size Determination - Neuroimaging Sub-Study

We plan to test hypotheses at a global 5% Type I error (alpha) for each family of hypotheses, and have chosen a completed sample ($N=60$) that will achieve at least 80% power using 2-sided tests. Our analysis of power was based on “effect size” (standardized difference). Effect sizes were calculated from our own preliminary data, from published data summaries, and from published estimates of effects (e.g., t statistics, coefficients, p-values) using validated summary methods. We have several hypotheses and more than one outcome measure for some (e.g., different brain regions). We will control error in a family-wise manner, adjusting alpha (Bonferroni Aims 1 and 2, Hochberg step-up procedure for Aim 3) for the number of tests within each hypothesis family. Bonferroni corrections will also be adjusted for the correlations among multiple outcomes.

Aim 1 includes 2 hypotheses (**H1a&b**) regarding treatment effects on neural responses including 5 ROIs responding to food-related tasks. We test at $p<0.02$ because of the high correlation among ROIs within subjects ($\rho=0.54$). Estimates of effect size from our center data ($d=0.36$) indicate that we have 80% power to detect the effects. Aim 1 also tests hypothesis **H1c** for cessation effects. At the Bonferroni corrected threshold of $p=0.0167$, we have 80% power to detect small to medium effect sizes ($d=0.37$).

Aim 2 (H2a&b) essentially tests for mediation. The hypothesis that cessation increases food intake will be tested at 0.05, with power for effect sizes $\sim d=0.32$ [9, 58]. For Aim 2b (ROIs predicting food intake), we expect a weaker correlation than H1a ($\rho=0.4$), and our adjusted threshold for significance is $p<0.01$. Expected effect sizes are approximately 0.5, and we expect 96% power to detect the effects.

Aim 3 begins with the model in Aim 2b above, and tests interacting effects of working memory-related BOLD signal and food reinforcement (or food cue reactivity) on food intake. We will reduce the complexity of this analysis by using difference scores (pre minus post) to model a 2-

CONFIDENTIAL

This material is the property of the University of Pennsylvania. Do not disclose or use except as authorized in writing by the study sponsor

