way interaction between working memory and food reinforcement on food intake. We will only test for brain ROIs found to be sensitive to treatment in Aim 1, the number of tests for interaction is uncertain. We anticipate that these effects will be positively correlated and will use the Hochberg step-up procedure, which is robust to correlations among outcomes in the range we expect. For purposes of power calculation, we assumed a correlation of 0.5, which resulted in a corrected p-value of 0.02 for 5 tests. Keeping the independent variables continuous, we can detect an interaction term (one-sample per subject, standardized) of $d=0.36$ with 80% power. Literature estimates for similar interactions were 0.65, 0.66, and 0.35. The lowest estimate gives 77% power, and the average (0.55) yields 98% power.

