Aim 3: Test whether cessation-induced working memory deficits moderate the relationship between neural responses to food cues and reinforcement and food intake: This implies a 3-way interaction for a repeated measures analysis (e.g. cessation condition by food reinforcement by working memory on food intake). We will reduce the complexity and eliminate the repeated measures by conducting the analysis using difference scores (pre vs post), and will use multiple linear regression to analyze the differences in food intake. We will model the brain responses to cue reactivity and to food reinforcement separately. The models will contain a term for the difference in BOLD signal, and we will introduce a candidate moderator.

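### Neuroimaging Aim 3 states its moderator as a level of working-memory activity, but the analysis names only pre-minus-post differences and never fixes the moderator's scale

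*Combined protocol and SAP*

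**What the plan says.** **Section 2.2 (objectives).** Aim 3 asks whether treatment-induced change in food-related neural response "is a stronger predictor of food intake among smokers with greater cognitive control". The prediction beneath it locates the stronger relationship "among smokers who also show greater working memory-related neural activity (i.e., DLPFC BOLD signal) at baseline and post treatment". Section 1.2 also words the aim in terms of greater cognitive control. These statements describe how high a person's activity is, not how much it moves.

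**Section 6.8 (sample size).** The wording is "We will reduce the complexity of this analysis by using difference scores (pre minus post", and the scores serve to model a two-"way interaction between working memory and food reinforcement on food intake". No other scale is named there.

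**Section 6.11 (statistical methods).** Aim 3 is headed "Test whether cessation-induced working memory deficits moderate the relationship between neural responses to food cues and reinforcement and food intake". A deficit induced by cessation is a change. The section then says "We will reduce the complexity and eliminate the repeated measures by conducting the analysis using difference scores (pre vs post", with multiple linear regression on the differences in food intake. The model is described in one sentence: "The models will contain a term for the difference in BOLD signal, and we will introduce a candidate moderator". Whether that moderator is a Scan 1 value, a Scan 2 value, an average or a difference is not stated.

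**The concern.** Level and change are different moderators. Someone with high DLPFC activity at both scans and someone with low activity at both scans have the same pre-minus-post score, about zero, although section 2.2 predicts opposite things for them.

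If working memory enters as a difference, a null interaction could be reported as evidence that cognitive control does not moderate the effect, when the model had little chance of showing it. A positive interaction would support a claim about change in working-memory activity. The closing paragraph of section 2.2 says that support for the cognitive control hypothesis could point to adding neurocognitive training to BAS+. That inference needs the level result.

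**Working it through.** **Step 1. The plan's own power figure.** Section 6.8 gives 80% power for a standardized interaction of 0.36, 77% for 0.35 and 98% for 0.55, with N=60, two-sided tests and a corrected p-value of 0.02. The formula for one standardized value per subject is power = Φ(d√N − z), with √60 = 7.746.

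- d = 0.36, alpha 0.02: 0.36 × 7.746 − 2.326 = 0.462, so 67.8%.
- d = 0.35 and 0.55, alpha 0.02: 65.0% and 97.3%.
- The same three at alpha 0.05: 79.6%, 77.4% and 98.9%.

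The first two stated figures therefore match alpha 0.05 rather than 0.02. That is a separate matter, and nothing below depends on it.

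**Step 2. What the difference score knows about level.** Let D = pre − post, let ρ be the pre/post correlation, and let the mean be (pre + post)/2.

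- Cov(mean, D) = (Var pre − Var post)/2. This is zero when the two SDs are equal.
- With equal SDs, corr(D, pre) = √((1 − ρ)/2), and corr(D, post) is the same with a minus sign. At ρ = 0.6 this is √0.2 = 0.45. At ρ = 0.3, 0.5 and 0.7 it is 0.59, 0.50 and 0.39.
- With post/pre SD ratios of 0.9 to 1.1, corr(D, mean) runs from about −0.13 to +0.15. With ratios of 0.8 to 1.25 it reaches about ±0.30, and its sign depends on which SD is larger.

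So D is nearly uninformative about the two-scan mean when the SDs are similar. It is a weak proxy for either single-scan level, with opposite signs for the two scans.

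**Step 3. What that does to detection.** Inputs from section 6.8 are N=60, alpha 0.02 and interactions of 0.36 and 0.55. Assumed, because the documents give no values, are ρ = 0.6, equal SDs, standardized normal predictors and residual SD 1. Outcomes were simulated with a level as the true moderator. The regression (both main effects plus product term) was then fitted with either D or that level as the moderator.

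| True moderator | Interaction | D entered | Level entered |
|---|---|---|---|
| Two-scan mean | 0.36 | about 3% | about 56% |
| Two-scan mean | 0.55 | about 4-5% | about 90% |
| Scan 1 level | 0.36 | about 13% | about 57% |
| Scan 1 level | 0.55 | about 26% | about 89% |

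The floor is the 2% type I error. The level column is below the 67.8% of Step 1 because a product term is being estimated in a regression with main effects.

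**Step 4. Sensitivity.**

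- *Correlation.* For ρ from 0.3 to 0.7 at interaction 0.36, D stays at about 3% for the two-scan mean. For a single-scan level it runs from about 9% to 20%.
- *Unequal SDs.* With ratios of 0.8 or 1.25, the 3% at interaction 0.36 rises only to about 6%. At 0.55 it is no more than about 13%.
- *Sample size.* At N=50, the figure in section 3.2, D detects two-scan-mean moderation about 3-4% of the time, against about 48% (0.36) and 82-83% (0.55) with the level.
- *Alpha.* At alpha 0.05, N=60 and interaction 0.36, the two-scan-mean figures are 6-8% against 71-72%.

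**The case against.** A reader might infer that the stated moderator is simply not tested. The text does not go that far. In section 6.11 the difference in BOLD signal follows a sentence about cue reactivity and food reinforcement, so it can refer to the food-task term alone, with the moderator listed apart from it and its scale open. Section 6.8 uses difference scores to model the interaction but does not expressly say that working memory is differenced. Differencing intake and food-task BOLD would already remove the repeated measures. This objection stands: differencing working memory is the most natural reading of section 6.8, not a stated fact. It does not clear the plan, because no section specifies a level in the analysis, and a moderator without a defined scale needs the same correction.

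A reader might also infer that a difference score carries no information on level. That is true only of the two-scan mean with equal SDs. The SDs may differ, since section 6.2.13 puts Scan 1 about 30 minutes after a cigarette and Scan 2 late in patch treatment with the patch removed. At ρ = 0.6 and equal SDs the score also correlates 0.45 in size with each single-scan level. The 3-5% figure must therefore not be quoted as the general case. Because the two signs are opposite, a significant coefficient would still not tell high baseline activity from low post-treatment activity.

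Nor does section 2.2 call for the mean of the two scans. It names both time points and no average, so two separate level analyses fit its words equally well.

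Finally, change may be what was meant: section 1.2 argues that cessation impairs executive function, which gives the deficit moderator a rationale. In that case sections 1.2 and 2.2 state the wrong aim, and the sections still have to be reconciled.

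**Conclusion.** The point holds as an unreconciled conflict. Section 2.2 asks about level, section 6.8 names only differences, and section 6.11 speaks of a deficit while leaving the moderator's scale undefined. If working memory is differenced, the model is a poor test of the stated hypothesis. Detection is close to the type I error rate if the two-scan mean is the true moderator, and less than a third of what the level would give if baseline is (13/57 = 0.23; 26/89 = 0.29).

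These sizes rest on an assumed correlation and assumed SDs. The ranges tried change the figures but not the conclusion. This is the third aim of a sub-study and touches no primary outcome of the parent trial, so the correction is advisable rather than critical.

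**What to change.** Write out the Aim 3 regression. Keep difference scores for food-task BOLD and for food intake, and enter working memory as a level, with its main effect and its product with the food-task difference.

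- **Primary moderator:** Scan 1 DLPFC n-back BOLD. Section 6.2.13 places Scan 1 before the Baseline Visit, where the first counseling session is held, so this value precedes treatment.
- **Supporting analysis:** the Scan 2 level or the two-scan mean, to cover the post-treatment part of the prediction in section 2.2. Either may be affected by treatment and should be read with that in mind.
- **Secondary moderator:** the working-memory change score, reported separately as the answer to the deficit question in section 6.11.
- **Alignment:** use the same moderator definition in sections 2.2, 6.8 and 6.11, including the section 6.11 heading.

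The cost is revised wording and one extra moderator analysis. Table 1 includes the working-memory task in the scan session used at both visits, so no new data are needed. The change does not by itself reach 80% power at an interaction of 0.36: with the level entered, the simulated figure at N=60 and alpha 0.02 is about 56-57%.

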3.2 General Design - Neuroimaging Sub-Study

We propose to study a sub-sample of consecutively recruited participants (N=~50) enrolled in the parent randomized clinical trial. As displayed in **Figure 2**, an equal number of fMRI eligible smokers from the BAS+ or SC treatment group will be studied before treatment (~week -2) and during the final week of nicotine patch therapy (~week 7-8). As part of the parent study, smoking will be assessed by self-report and biochemically confirmed weekly after quitting, at EOT (week 8), and at the 12 and 26 week follow-ups. Weight will be assessed at these same time points. Food intake will be measured by three consecutive days of 24-hour food recalls at baseline and 4-, 8-, 12- and 26-weeks post-TQD.

Scans identified in **Figure 2** and included within the Study Procedures Section represent approximations. Participants will complete scans as designated in Figure 2 and the Study Procedures, but will be permitted a degree of flexibility at the discretion of the Principal Investigator due to extenuating circumstances.

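### Neuroimaging Aim 3 power is stated as if every brain region were tested, but a region is tested only if it first passes an undefined Aim 1 screen

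*Combined protocol and SAP*

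**What the plan says.** Section 6.8, under Aim 3, limits the interaction tests to regions of interest (ROIs) that did well in Aim 1: "We will only test for brain ROIs found to be sensitive to treatment in Aim 1". The same sentence admits that their number is open. Section 2.2 has a similar rule on a different basis: "Regions of interest for food cue and choice-related neural activity will be selected from those shown to be sensitive to cessation in Aim 1". The Aim 3 methods in section 6.11 mention no screen.

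For power, 6.8 assumes a correlation of 0.5 among the tests, "which resulted in a corrected p-value of 0.02 for 5 tests". It then states 80% power for a one-sample standardized interaction of 0.36, 77% at 0.35 and 98% at 0.55.

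For Aim 1, 6.8 sets p<0.02 for five ROIs with correlation 0.54 and claims 80% power at d=0.36. Section 6.11 makes the Aim 1 comparisons between-subject, tested on the main effect of group.

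The sample size differs between sections. Section 6.8 says the investigators "have chosen a completed sample ($N=60$) that will achieve at least 80% power using 2-sided tests", while section 3.2 says "We propose to study a sub-sample of consecutively recruited participants (N=~50) enrolled in the parent randomized clinical trial". Section 3.2 also specifies equal numbers from each arm.

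**The concern.** Under the rule in 6.8, a region contributes to Aim 3 only if two things happen: it passes the Aim 1 screen, and its interaction test is then significant. The stated power covers only the second step. A reader would take 77% to 98% as the chance that Aim 3 finds a real moderation effect in a given region, but the procedure described offers less, by an amount that depends on how often a truly responsive region passes.

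The screen is also not fixed. Treatment and cessation are different contrasts (between arms, or before versus after quitting), and neither section gives a criterion. Two analysts could legitimately test different sets of regions, from none to all. Aim 3 could go untested although moderation exists, and the choice of regions could be questioned afterwards.

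**Working it through.** **Inputs.** Two-sided alpha 0.02 for both aims (6.8), so z = 2.326. Aim 1 effect d = 0.36 (6.8). Completed sample 50 (3.2) or 60 (6.8), so 25 or 30 per arm. Correlation among Aim 1 ROIs 0.54 (6.8). Assumptions: passing the screen means p<0.02, and d is standardized to the analysed outcome.

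**1. The plan's own Aim 3 figures.** One-sample normal power is Phi(d x sqrt(N) - z). With N=60, sqrt(N) = 7.746:
- d=0.35: Phi(2.711 - 2.326) = 65% (stated 77%)
- d=0.36: Phi(2.789 - 2.326) = 68% (stated 80%)
- d=0.55: Phi(4.260 - 2.326) = 97% (stated 98%)

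The two lower figures do not follow from N=60 at 0.02. They come out with N of about 77 (77% and 80%), or with N=60 at an uncorrected 0.05 (77% and 80%). That is a separate matter. The stated figures are used below, which favours the plan.

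**2. Screen read as the between-arm Aim 1 test.** Normal power is Phi(d x sqrt(n/2) - z), with n per arm:
- n=25: Phi(0.36 x 3.536 - 2.326) = Phi(-1.054) = 14.6%; noncentral t gives 13.8%
- n=30: Phi(0.36 x 3.873 - 2.326) = Phi(-0.932) = 17.6%; noncentral t gives 16.8%

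A region must enter to be tested, so by the t-test figures its Aim 3 power cannot exceed 14% to 17%, whatever the dependence between the steps. Simulating five regions, all at d=0.36 with correlation 0.54, no region enters in 62% to 66% of trials (25 per arm) or 57% to 60% (30 per arm), depending on the approximation. On average fewer than one of the five enters.

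Baseline adjustment helps somewhat if d is in raw SD units. With an assumed pre-post correlation r, the effective effect is 0.36/sqrt(1 - r^2): 0.416 at r=0.5 and 0.504 at r=0.7. Entry is then about 20% to 29% (25 per arm) or 24% to 35% (30 per arm), by the normal formula.

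**3. Screen read as a within-subject pre-post test.** One-sample noncentral t at d=0.36 gives 56% (N=50) or 65% (N=60). Multiplied by the stated 77% to 98%, that is 0.56 x 0.77 = 43% up to 0.65 x 0.98 = 64%.

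**4. Aim 1's stated 80% accepted.** 0.80 x 0.77 = 62%, 0.80 x 0.80 = 64%, 0.80 x 0.98 = 78%.

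| Reading of the screen | Chance of entry at d=0.36 | Entry x stated Aim 3 power |
|---|---|---|
| Between-arm, p<0.02 | 14% to 17% | 11% to 16% |
| Within-subject, p<0.02 | 56% to 65% | 43% to 64% |
| Aim 1's stated power | 80% | 62% to 78% |

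The products are exact if the stated figures mean power given entry. If they mean the power of the interaction test ignoring the screen, the products assume that the two steps are independent.

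**The case against.** Several points on the other side carry weight.

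- A reader might infer that the plan treats a non-significant region as proven insensitive. The documents do not say so. They only restrict which regions are tested, and such a restriction also limits multiplicity.
- A reader might infer that the screen is irrelevant to Aim 3. Section 2.2 frames Aim 3 around change in neural response induced by BAS+ relative to SC, so requiring some arm effect fits the stated hypothesis. The model in 6.8 and 6.11 is simpler, a BOLD change by working memory interaction on intake, and that can exist in a region with no mean arm difference. Dropping the screen is therefore defensible, but it is partly a design choice.
- The p<0.02 between-arm criterion is inferred, and the result depends strongly on it, as the table shows.
- Much of the 14% to 17% ceiling comes from Aim 1 itself: a between-arm test with 25 or 30 per arm does not have 80% power at d=0.36. It would be wrong to attribute the whole shortfall to the screen.
- Section 6.8 concedes that the number of tests is uncertain and plans at the five-test threshold. That handles multiplicity, but not the chance of entry.

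These points narrow the concern without removing it. The power statement still omits the screen, and the screen is still undefined.

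**Conclusion.** The stated Aim 3 power does not describe the screened procedure. At the plan's Aim 1 effect, the chance of entry alone is below every stated figure under the between-arm reading (14% to 17%) and the within-subject reading (56% to 65%), with no independence assumption. If Aim 1's 80% is accepted, joint power is about 62% to 78% under independence, each value below its stated counterpart. In that case strong positive dependence could close most of the gap at the two smaller effects, but 98% could not be reached because entry caps it at 80%.

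The documents do not support concluding that Aim 3 has at most 17% power outright. That holds only for a between-arm p<0.02 screen and a true effect of 0.36; a larger true effect or baseline adjustment raises it. The issue is confined to the third aim of a mechanistic sub-study and leaves the trial's primary outcomes untouched.

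**What to change.** **Minimum.** In 6.8, restate Aim 3 power as the probability of passing the screen and detecting the interaction, or label the present figures as conditional and give the entry probability beside them. Reconcile 2.2 and 6.8 on whether the screen concerns treatment or cessation, state its criterion, and carry it into 6.11. Use one completed sample size (about 50 or 60) throughout. This costs wording and a short calculation.

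**Preferred.** Because 6.8 already plans at a five-test threshold, run the Aim 3 interaction under Hochberg in all pre-specified ROIs regardless of their Aim 1 result, and name them in 6.11. The lists must first agree:
- Section 2.2 gives insula, ACC, OFC and VS/NAC for cues, and VS/NAC and vmPFC for choice. That is five regions but six region-by-task pairs.
- Section 6.5.6 has caudate, and not VS/NAC, among the cue regions.
- Section 6.11 makes VS and vmPFC primary for both tasks and lists OFC and insula as secondary.

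The working-memory region used as moderator should be fixed at the same time. If the agreed family is not five tests, the planning threshold of 0.02 needs recalculating. The cost is a few more regressions on data already collected and a slightly broader question than change induced by BAS+.
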